### **Cognition**

The following cognition parameters will be presented by treatment group in summary tables. Results on the cognitive subdomains will only be presented in listings.

- Proportion of patients with a change of  $\geq 8$ ,  $\geq 4$ , and  $\geq 9$  for ALS Specific, ALS Non-Specific, and ECAS (Edinburgh Cognitive and behavioral ALS Screen) total score;
- Absolute values and change from baseline for ALS Specific, ALS Non-Specific, and ECAS total score at 24, 48 and 72 weeks.
- Time to a mean change of  $\geq 8$ ,  $\geq 4$ , and  $\geq 9$  for ALS Specific, ALS Non-Specific, and ECAS total score.

## **Pharmacokinetics**

The Population PK parameters of FAB122 and riluzole will be presented by the PK vendor, and analysis is specified in a separate PK analysis plan. A separate PK report may be created by the PK vendor and added to the Clinical Study Report.

### **5.6.3 Additional analysis**

As an additional (supportive) analysis, the joint assessment of change in functional decline and overall mortality using a joint modelling (i.e. shared-parameter) framework over 48 weeks (all patients) and 72 weeks (subgroup of 100 patients) will be determined. The statistical model will combine ALSFRS-R score and survival, using a linear mixed model and a Cox model, as submodels combined into a non-linear mixed model using the SAS procedure PROC NLMIXED. Parameter estimates and standard errors will be presented. Initial values for the parameters in the joint model may be based on the resulting parameter estimates of the two submodels, as described before for ALSFRS-R and survival. Example SAS code is available as reference in the publication of Vonesh e.a., 2006.

### **5.6.4 Exploratory analysis**

#### PK analysis

All summary tables, plots, listings, and analyses of the PK concentration data and parameters will be done by the PK vendor. PK listings containing the dates and times of the sample collection will be created by Certara.

The data for the PK concentration and the calculated PK parameters received according to the agreed data transfer specifications may be converted to CDISC format by Certara (if not done by the PK vendor) and can be supplied back to the PK scientist for use in the PK analyses.

#### Biomarkers

The following biomarkers will be summarized by treatment group as exploratory endpoints:

- Change from baseline in the prognostic ALS biomarker neurofilament light (NFL)
- Change from baseline in the ALS biomarkers creatinine and creatinine kinase
- Change from baseline in the ALS biomarker Urinary extracellular domain of neurotrophin receptor p75 (Urinary P75ECD)
- Change from baseline of oxidative stress biomarker 8-hydroxyguanosine (8-OHdG)

For NFL also the geometric mean and geometric mean ratio will be presented, using log-transformed (based on natural logarithm) data. The geometric mean is calculated as the exponent of the mean of the log transformed data. The geometric mean ratio is the ratio of two geometric means.

Furthermore, a listing will be created presenting all data that are out of reference range on a per-patient level, including any available unscheduled measurements. The investigator has judged the out-of-range values on their clinical significance, and this information will be added as well. Information regarding age at screening and gender will be added to this listing.

---

 R.P.A. van Eijk et al. Joint modeling of endpoints can be used to answer various research questions in randomized clinical trials. Journal of Clinical Epidemiology 147 (2022): 32-39

### Cost-utility analysis

In this study, an exploratory cost-utility analysis for treatment with FAB122 will be conducted based on the data from the cost questionnaire providing direct and indirect costs associated with the disease, and information from eCRF data existing of hospitalizations, concomitant medication and occurrence of AEs.

The following cost parameters are considered for the cost-utility analysis among study groups:

- Number of contacts classified per specialist and type of contact.
- Number of hospitalizations related to ALS classified per unit of stay and length of stay.
- Specialized equipment / Devices cost per type of Medical Aid.
- Paramedical treatment visits (i.e. physical therapy, rehabilitation, occupational therapist, speech and language therapist, or otherwise specified by the patient).
- Formal care (i.e. health professional) and informal care (i.e. familiar/friend): duration and cost per type of service and overall.
- Employment situation.
- Occurrence of AEs in each group (see section 5.7.1, note: no costs are collected for this).

Descriptive statistics will be displayed for each of the categories above as well as for the costs by category and over all categories for each patient, where costs will be presented in euros. As applicable, duration of a hospitalization (in days) will be presented as average over the patients as well as the total summed duration over all patients per treatment group. Adding of costs and calculation from local tariff to euro will be done via programming, using input from client and DM vendor on used currency and exchange rates to be used by time of Database lock.

It should be noted that most cost-utility analysis fields are free text (in local language), which may make it complicated to derive all the above directly from the data. Also, in the data collected, there is no clear indication whether or not hospitalizations are related to ALS and total costs collected are not consistently entered. Specific data handling strategies may be discussed with the client and the DM vendor, otherwise descriptive statistics will be limited to items as collected, where free text fields will only be listed (without translation).

## **5.7 Safety and tolerability evaluation**

All safety presentations will be created using the SAF population.

### **5.7.1 Adverse events**

A treatment emergent adverse event (TEAE) is defined as an adverse event that appears during or after first study treatment. In case of (partially) missing start/stop dates, refer to Section 5.2.

An AE overview table will be created displaying the number of patients (and percentage) experiencing a treatment-emergent adverse event (TEAE) and the number of TEAEs for: Any TEAE, Any mild/moderate/severe TEAE, Any unrelated/related TEAE, Any serious AE, Any serious TEAE, and Any TEAE leading to study discontinuation.

SUSARs will be reported by the pharmacovigilance vendor.

All TEAEs are tabulated by System Organ Class (SOC) and Preferred Terms (PTs) within each SOC according to the MedDRA terminology list. TEAEs will also be tabulated by severity (mild/moderate/severe) and by relationship to study medication (related/unrelated), using frequency counts (number of patients with at least one event, and number of events) and percentage of patients with the event. Similar tables will be created for TEAEs leading to

premature discontinuation, Serious TEAEs and TEAEs of special interest. These summary tables will be presented by decreasing frequency of occurrence based on SOC and PT.

The summary tables will be accompanied by individual patient listings of *all* AEs including information on AE number, actual AE description, date of start and end of AE (or ongoing), PT (MedDRA), SOC (MedDRA), severity, relationship, pre-existing (yes/no), seriousness, special interest, action taken and outcome. Pre-existing AEs are not considered to be treatment emergent. AEs starting prior to administration of the study drug will only be listed.

Separate listings will be created for AESIs, SAEs, and deaths.

For summary tables, an AE is considered related if the causality to the study medication is classified as either ‘Probably Related’ or ‘Possibly Related’, where a missing relationship is also considered related. Otherwise, it will be considered unrelated for summary tables. The original description will be used in listings.

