#### 6.5. Early Discontinuation/Withdrawal of Participants

Subjects may withdraw consent at any time for any reason or be dropped from the trial at the discretion of the investigator should any untoward effect occur. In addition, a subject may be withdrawn by the investigator or the Sponsor if enrolment into the trial is inappropriate, the trial plan is violated, or for administrative and/or safety reasons.

In this trial, a subject may discontinue from treatment but continue to participate in the regularly scheduled activities, as long as the subject does not withdraw consent. Once a subject has discontinued treatment, he/she may be allowed to start treatment again after consultation with the investigator, if discontinuation of treatment is  $\leq$  2 weeks.

A subject must be discontinued from the trial for any of the following reasons:

- The subject withdraws consent.
- The subject has a medical condition or personal circumstances which, in the opinion of the investigator and/or Sponsor, places the subject at unnecessary risk if participation in the trial is continued.
- The subject reaches the criteria for respiratory insufficiency (tracheostomy or the use of non-invasive ventilation for >20 hours per day for >10 consecutive days),

A subject must be discontinued from study treatment (but should continue to be monitored in the study) for any of the following reasons:

1-The subject becomes pregnant during the study.

2-The subject's investigator considers it is in the best interest of the subject to discontinue including worsening or disease progression if the investigator considers that it is in the patient's best interest the initiation of any standard of care treatment prohibited in the study

3-Serious adverse event considered related to the IMP

4-Severe Neurotoxicity considered related to the IMP

5-Any other severe adverse event considered related to the IMP at the discretion of the investigator.

6-Acute renal failure (creatinine clearance of less than 30 mL/min as calculated by the Cockcroft Gault equation)

7-Severe liver disorder defined as:

- ALT/AST  $\geq$  3xULN and bilirubin  $\geq$  2xULN ( $>35\%$  direct bilirubin)
- ALT/AST  $\geq$  8xULN
- ALT/AST  $\geq$  3xULN and with symptoms believed to be related to liver injury or hypersensitivity.
- ALT/AST  $\geq$  3x baseline ALT/AST and with symptoms believed to be related to liver injury or hypersensitivity.

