#### 11.3.6. Safety Analysis

Safety evaluations will be based on the incidence, severity, and type of AEs and clinically significant changes in the subject's physical examination findings, vital signs, and clinical laboratory results. Safety variables will be tabulated and presented for all subjects in the Safety Population. Data will be summarized by treatment and time. Exposure to study drug and reasons for discontinuation of study drug will be tabulated.

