### 11.4. Study Estimand and Handling of Missing Data

To be noted that in this study all efforts will be made to ensure collection of data up to week 48 for all randomized subjects and at least for 100 subjects up to week 72 regardless of treatment withdrawal or protocol deviations.

As per the ICH E9(R1) (*draft addendum on estimands and sensitivity analysis in clinical trials*), the plan for the assessment of the Primary endpoint (PEP) is described here after using the 4 attributes of the estimand:

1. Population: ALS patients fulfilling the selection criteria, as described in section 5 of this protocol
2. Primary endpoint (PEP): Change from baseline in Amyotrophic Lateral Sclerosis Functional Rating Scale – Revised (ALSFRS-R) score after 48 weeks (see sections 3.2.1 and 11.3.4.1)
3. Intercurrent events (IE): The assumptions and expectations on the relevant intercurrent for this study have been based on the publication of a similar trial (Cudkowicz et al., 2013)
4. Accordingly, the following situations have been identified:
  - a. No treatment initiation with the IMP: exclusion from the main analysis with the mFAS population.
  - b. Treatment discontinuation because of adverse events: expected rates  $\approx 3$  (control arm) - 7% (experimental arm).
  - c. Treatment discontinuation because of lack of efficacy: expected rates  $\approx 5$  (control arm) 10% (experimental arm).
  - d. Other treatment related reasons (i.e. due to efficacy or safety issues). To this category will apply other treatment related reasons that those specified in "b" and "c", even that, *a priori*, no potential scenarios are foreseen at the moment of the planning.
  - e. Rescue medication. No clear prevalence rates can be ascertained, but differential higher rates are expected in placebo. This situation is likely to be closely related to IE #c.
  - f. Non treatment-related reasons, others than specified in this list of IE: very low expected rates (i.e.  $\le 1\%$ ). This will also situations like patients moving (not because bad prognosis) to another location or death for completely treatment-unrelated reasons.
  - g. Related death (or death with unknown reasons): it is expected that the rate of death at 52 weeks will be lower than the observed in that trial ( $< 17\%$ ). A non-substantial but lower rate is expected in the experimental arm.

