## **4.5 Safety endpoint(s)**

- Nature, frequency and severity of Treatment Emergent Adverse Events;
- Parameters derived from vital signs and 12-lead electrocardiogram (ECG);
- Parameters derived from laboratory tests (hematology, biochemistry, urinalysis);
- Proportion of subjects that drop out due to adverse events.

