14.2.16.2	Statistical analysis results for HDD mega score	
14.2.17.1- 14.2.17.6	Descriptive statistics for Quality of Life: ALSAQ-40 (total score and 5 scales)	
14.2.17.7	Statistical analysis results for Quality of Life: ALSAQ-40 total score	
14.2.17.8	Descriptive statistics for Quality of Life: EQ-5D-5L	
14.2.17.9	Descriptive statistics for Quality of Life: VAS	
14.2.17.10	Statistical analysis results for Quality of Life: VAS	
14.2.18.1- 14.2.18.x	Descriptive statistics for Cognition (ECAS)	
14.2.19.1- 14.2.19.x	Descriptive statistics for Biomarkers	
14.2.19.5	Out of range Biomarkers	

14.2.20.1- 14.2.20.x	Descriptive statistics for Cost-Utility analysis	
14.3 Safety Data Summary figures and tables – 14.3.1 Displays of Adverse Events		
14.3.1.1	Overview adverse events	X
14.3.1.2	Treatment emergent adverse events	X
14.3.1.3- 14.3.1.5	Treatment emergent adverse events by severity	X
14.3.1.6- 14.3.1.7	Treatment emergent adverse events by relationship	X
14.3.1.8	Treatment emergent adverse events leading to premature discontinuation	X
14.3.1.9	AESIs	X
14.3.1.10	SAEs	X
14.3 Safety Data Summary figures and tables – 14.3.2 Listings of Deaths, Other Serious and Significant Adverse Events		
14.3.2.1	AESIs	
14.3.2.2	SAEs	
14.3.2.3	Deaths	
14.3 Safety Data Summary figures and tables – 14.3.4 Abnormal Laboratory Value Listing (each patient)		
14.3.4.1	Out of range clinical laboratory	
14.3.4.2- 14.3.4.7	Descriptive statistics Clinical laboratory – haematology, clinical chemistry, urinalysis, serology, vitamin B6	
14.3.4.8.1	Descriptive statistics Vital signs	
14.3.4.8.2	Mean (SD) plot Vital signs	
14.3.4.9.1	Descriptive statistics ECG	
14.3.4.9.2	Mean (SD) plot ECG	
14.3.4.10	Physical Examination	
14.3.4.11.1- 14.3.4.11.x	Nerve Conduction Study	
14.3.4.12- 14.3.4.13	Prior and concomitant medication	

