## 10.4 Listings

Following ICH E3 guidelines, all listings mentioned here will be presented in Section 16.2 of the CSR, and listings will be prepared in the order and with section number as stated.

Individual listings will be prepared of all the data collected in the database, following SDTM data format. No combining of data other than mentioned in this paragraph will be performed. The key variables in the listings (except a few displaying screening data) will be patient number and treatment. If applicable, visit number will be listed additionally. Furthermore, a listing containing study visit dates will be presented.

Listing number	Contents of listing
16.2.1 Discontinued patients	
16.2.1.1	Inclusion/exclusion criteria – description
16.2.1.2	Inclusion/exclusion criteria – deviations
16.2.1.3	Patient disposition
16.2.2 Protocol deviations	
16.2.2	Protocol deviations
16.2.3 Demographic and baseline data	
16.2.3.1	Demographics
16.2.3.2	Randomization
16.2.3.3	Substance use
16.2.3.4	Medical history
16.2.3.5	ALS history
16.2.3.6	Pregnancy test
16.2.4 Compliance and/or treatment data	
16.2.4.1	Treatment exposure
16.2.4.2	Drug accountability and compliance
16.2.4.3	Study visits
16.2.5 Individual efficacy response data	
16.2.5.1	ALSFRS-R
16.2.5.2	CAFS

16.2.5.3	King's staging system
16.2.5.4	MiToS
16.2.5.5	SVC
16.2.5.6	HDD
16.2.5.7	QoL
16.2.5.8	Cognition (ECAS)
16.2.5.9	Biomarkers
16.2.5.10	Cost-utility
16.2.5.11	Survival
16.2.6 Adverse event listings	
16.2.6.1	Adverse events
16.2.6.2	AEs leading to discontinuation from the study
16.2.6.3	Vital signs
16.2.6.4	ECG
16.2.6.5	Physical Examination
16.2.6.6	Neurological examination
16.2.6.7	Nerve conduction study
16.2.6.8	Prior and concomitant medication
16.2.7 Listing of individual laboratory measurements by patient	
16.2.7.1	Laboratory safety data – haematology
16.2.7.2	Laboratory safety data – clinical chemistry
16.2.7.3	Laboratory safety data – urinalysis
16.2.7.4	Laboratory safety data – coagulation
16.2.7.5	Laboratory safety data – serology
16.2.7.6	Laboratory safety data – Vitamin B6
16.2.7.7	General comments

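### The SAP's adverse-event overview row and discontinuation listing count only events leading to study discontinuation, so they miss adverse-event-driven drug stops in patients who stay on study

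*SAP*

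**What the plan says.** The fourth safety endpoint, in Protocol 3.2.3 and again in SAP 4.5, is "Proportion of subjects that drop out due to adverse events". Neither document says whether dropping out means stopping study drug or leaving the study.

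The SAP plans three adverse-event outputs on discontinuation:

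- The overview table in 5.7.1 ends with "Any serious AE, Any serious TEAE, and Any TEAE leading to study discontinuation".
- Table 14.3.1.8 in 10.3 is titled "Treatment emergent adverse events leading to premature discontinuation".
- Listing 16.2.6.2 in 10.4 is titled "AEs leading to discontinuation from the study".

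The protocol treats the two events as different. In section 6.5, "a subject may discontinue from treatment but continue to participate in the regularly scheduled activities, as long as the subject does not withdraw consent". The same section then sets out a list under the words "A subject must be discontinued from study treatment (but should continue to be monitored in the study) for any of the following reasons". That list includes related serious adverse events, severe related neurotoxicity, and liver, renal and haematological events. Protocol 11.3.6 also promises a drug-level summary: "Exposure to study drug and reasons for discontinuation of study drug will be tabulated".

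**The concern.** Where patients who stop drug are meant to remain under observation, an adverse event that ends treatment need not end participation. The overview row and the listing record only the second. A patient managed as Protocol 6.5 directs, taken off drug for a related event and then followed, would have a tolerability failure that neither output shows. The better the follow-up works, the less these two outputs say about tolerability.

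This bears on one of four stated safety endpoints. Protocol 2.2 reports neurological findings in animals at relatively low safety margins, and severe related neurotoxicity is on the list of reasons to stop drug while staying in the study. The table of events of special interest would show such cases, but not that they led to stopping drug. An imbalance between arms in stopping drug for adverse events could therefore be understated, or missing, in the summary where a reader would look for it.

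**Working it through.** **Step 1: what each output counts.**

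| Place | Event counted |
|---|---|
| Protocol 3.2.3, SAP 4.5 (endpoint) | Dropping out, undefined |
| SAP 5.7.1, overview row | Study discontinuation |
| SAP 10.4, listing 16.2.6.2 | Study discontinuation |
| SAP 5.7.1 and 10.3, Table 14.3.1.8 | Premature discontinuation, drug or study not stated |
| SAP 5.5.4, disposition | Reason for non-completion; footnote 3 defines completion by weeks of treatment |
| Protocol 11.3.3, disposition | Primary reason for discontinuation, for treatment and follow-up phases |
| Protocol 11.3.6 | Reasons for discontinuing study drug |

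The table list in SAP 10.3 contains no table of reasons for stopping study drug. SAP section 6, which records changes from the protocol, does not mention its absence.

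**Step 2: expected number of drug stops.** The documents give no expected count for the overview row, so there is no figure to reproduce. They do give the inputs.

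- Arm sizes: 200 FAB122 and 100 placebo (SAP 2.4).
- Rates: Protocol 11.4 has "Treatment discontinuation because of adverse events: expected rates" of about 3% in the control arm and 7% in the experimental arm.

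Expected drug stops = arm size × rate:

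- FAB122: 200 × 0.07 = 14
- Placebo: 100 × 0.03 = 3
- Total: 14 + 3 = 17, a difference of 7% − 3% = 4 percentage points

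**Step 3: how many the study-level outputs would capture.** Let s be the share of these patients who also leave the study because of the event. The documents do not give s, so it is an assumption and the full range is shown. Captured = 14s on FAB122 and 3s on placebo; missed = 17(1 − s).

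| s (assumed, same in both arms) | FAB122, of 200 | Placebo, of 100 | Captured | Missed |
|---|---|---|---|---|
| 0% | 0 (0%) | 0 (0%) | 0 | 17 |
| 25% | 3.5 (1.75%) | 0.75 (0.75%) | 4.25 | 12.75 |
| 50% | 7 (3.5%) | 1.5 (1.5%) | 8.5 | 8.5 |
| 75% | 10.5 (5.25%) | 2.25 (2.25%) | 12.75 | 4.25 |
| 100% | 14 (7%) | 3 (3%) | 17 | 0 |

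The visible difference between arms is 4s percentage points.

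**Step 4: unequal retention.** If s differs by arm, the order of the arms can change. With s = 25% on FAB122 and 75% on placebo, the row reads 7% × 0.25 = 1.75% against 3% × 0.75 = 2.25%. The lower figure then falls on the arm with more drug stops. This illustrates what is possible; nothing in the documents predicts it.

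**The case against.** The strongest reply is that leaving the study is a natural meaning of dropping out. On that reading the overview row tabulates the endpoint as worded. This stands as far as it goes, which is why the remedy is to have the sponsor state the meaning and report both counts.

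A second reply is that drug stops may appear elsewhere. Table 14.3.1.8 uses different words from the overview row and may be meant to cover them. Footnote 3 to SAP 5.5.4 defines completion by weeks of treatment, so a patient who stops drug early but stays could count as a non-completer with an adverse event as the reason. The full adverse-event listing shows the action taken. These points stand in part. A reader might infer that study discontinuation is the only tabulation planned; the documents do not support that. But Table 14.3.1.8 is ambiguous, disposition gives a reason category without adverse-event terms, and a listing entry is not a summary by arm. The protocol's promise of a drug-level table does not help unless the SAP carries it.

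A third reply concerns size. A reader might infer that most of these drug stops would go uncounted, or that the row would read zero in both arms. Neither follows. Missing more than half needs s below 50%, and zero needs s = 0. Protocol 6.5 says that these patients should continue to be monitored, and section 4 has them followed as far as possible. Neither guarantees retention. Section 6.5 also lets the investigator drop a patient from the trial for an untoward effect, and both it and section 9 provide for withdrawal because of an adverse event.

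**Conclusion.** The point holds for the overview row in SAP 5.7.1 and for listing 16.2.6.2. As written, both omit drug stops for adverse events in patients who remain on study. No adverse-event output in the SAP is explicitly defined on discontinuation of study drug, and the drug-level table promised in Protocol 11.3.6 is not named.

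On the protocol's own expected rates, about 17 patients are at issue (14 against 3), and between 0 and 17 would be captured. That range rests on the planned arm sizes, on the rates in Protocol 11.4, and on a share leaving the study that the documents do not give. It does not support a claim about what proportion will be missed.

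The consequence is an incomplete descriptive account of tolerability. No hypothesis test depends on it, and individual cases should remain traceable through the action-taken entries in the full listing. The change is still worth making before database lock, because it costs little and concerns a stated endpoint.

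**What to change.** 1. In SAP 5.7.1, add an overview row for patients with at least one treatment-emergent event leading to permanent discontinuation of study drug. Keep the study-discontinuation row as a separate line.
2. In SAP 4.5, state which of the two dropping out refers to, and report both.
3. Produce Table 14.3.1.8 and listing 16.2.6.2 for discontinuation of study drug, with study discontinuation flagged separately.
4. Add to SAP 10.3 the table of reasons for discontinuing study drug from Protocol 11.3.6.

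No new data should be needed: Protocol 9.5 has the investigator record the action taken with study drug for every adverse event, and SAP 5.7.1 already lists that field. One detail to settle is the word permanent. Protocol 6.5 allows treatment to restart after a break of two weeks or less, and the documents do not show how the field separates a break from a final stop, so the derivation may need checking against the end-of-treatment date. The cost is SAP wording, one extra row and one extra table.
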